3.7.1.9 Acceptable Window for Testing

Observations/examinations and other procedures are to be performed within an acceptable window for testing, as specified in Table 3.7.1.9-1, with consideration of the availability of each subject for site visits, etc.

 Table 3.7.1.9-1
 Acceptable Window for Examinations/Assessment Period

The starting point of the antidepressant treatment period (Phase A) is the day of assessment at the initiation of the antidepressant treatment period (Phase A).

| Examination Point | Reference Day | Acceptable Window (From the Reference Day) |
|--|--|--|
| At screening | Day of assessment at the initiation of the antidepressant treatment period (Phase A) | Day -28 to -1 |
| Day of assessment at the initiation of the antidepressant treatment period (Phase A) | Day 1 | _ |
| Week 1 of the antidepressant treatment period (Phase A) | Day 8 | ± 2 days |
| Week 2 of the antidepressant treatment period (Phase A) | Day 15 | ± 2 days |
| Week 3 of the antidepressant treatment period (Phase A) | Day 22 | ± 2 days |
| Week 4 of the antidepressant treatment period (Phase A) | Day 29 | ± 2 days |
| Week 6 of the antidepressant treatment period (Phase A) | Day 43 | ± 2 days |
| Week 8 of the antidepressant treatment period (Phase A) | Day 57 | ± 2 days |
| At discontinuation | _ | _ |

At discontinuation: Performed within a possible window at a feasible time point.

 Table 3.7.1.9-1
 Acceptable Window for Examinations/Assessment Period

The starting point of the double-blind period (Phase B) is the day of assessment at Week 8 of the antidepressant treatment period (Phase A).

| Examination Point | Reference Day | Acceptable Window (From the Reference Day) |
|---|---------------|--|
| Day of assessment at Week 8 of the antidepressant | Day 1 | _ |
| treatment period (Phase A) | | |
| Week 1 of the double-blind period (Phase B) | Day 8 | $\pm 1 \text{ day}$ |
| Week 2 of the double-blind period (Phase B) | Day 15 | ± 2 days |
| Week 3 of the double-blind period (Phase B) | Day 22 | ± 2 days |
| Week 4 of the double-blind period (Phase B) | Day 29 | ± 2 days |
| Week 5 of the double-blind period (Phase B) | Day 36 | ± 2 days |
| Week 6 of the double-blind period (Phase B) | Day 43 | ± 2 days |
| At discontinuation | _ | _ |

At discontinuation: Performed within a possible window at a feasible time point.

The starting point of the antidepressant-responder treatment-continuation period (Phase A+) is the day of assessment at Week 8 of the antidepressant treatment period (Phase A).

| Examination Point | Reference Day | Acceptable Window (From the Reference Day) |
|---|---------------|--|
| Day of assessment at Week 8 of the antidepressant treatment period (Phase A) | Day 1 | _ |
| Week 1 of the antidepressant-responder treatment- continuation period (Phase A+) | Day 8 | ± 1 day |
| Week 2 of the antidepressant-responder treatment- continuation period (Phase A+) | Day 15 | ± 2 days |
| Week 3 of the antidepressant-responder treatment- continuation period (Phase A+) | Day 22 | ± 2 days |
| Week 4 of the antidepressant-responder treatment- continuation period (Phase A+) | Day 29 | ± 2 days |
| Week 5 of the antidepressant-responder treatment- continuation period (Phase A+) | Day 36 | ± 2 days |
| Week 6 of the antidepressant-responder treatment- continuation period (Phase A+) | Day 43 | ± 2 days |
| At discontinuation | - | _ |

At discontinuation: Performed within a possible window at a feasible time point.

The starting point of the post-treatment observation period is the day of the final IMP administration.

| Period | Reference Day | Acceptable Window (From the Reference Day) |
|-----------------------------------|---------------|--|
| Day of final IMP administration | Day 1 | _ |
| Post-treatment observation period | Day 31 | ± 5 days |

3.7.2 Efficacy Assessments

3.7.2.1 Montgomery Asberg Depression Rating Scale

(1) Time points

At the initiation and Weeks 2, 4, 6, and 8 (or discontinuation) of the antidepressant treatment period (Phase A), Weeks 1, 2, 3, 4, 5, and 6 (or discontinuation) of the double-blind period (Phase B), and Week 6 (or discontinuation) of the antidepressant-responder treatment-continuation period (Phase A+)

(2) Methods

A trained and qualified investigator or subinvestigator will assess the following 10 symptoms of depression in the subject on a 7-point scale (0 to 6) using SIGMA at the specified assessment time points, and record the date, time, and results of assessment in the source documents and the CRF.

Apparent sadness
 Reported sadness
 Inner tension
 Reduced sleep
 Reduced appetite
 Concentration difficulties
 Lassitude
 Inability to feel

9. Pessimistic thoughts 10. Suicidal thoughts

3.7.2.2 Clinical Global Impression – Improvement

(1) Time points

At Weeks 1, 2, 3, 4, 6, and 8 (or discontinuation) of the antidepressant treatment period (Phase A), Weeks 1, 2, 3, 4, 5, and 6 (or discontinuation) of the double-blind period (Phase B), and Week 6 (or discontinuation) of the antidepressant-responder treatment-continuation period (Phase A+)

(2) Methods

The investigator or subinvestigator will assess the improvement of depressive symptoms in the subject on the following 8-point scale using CGI-I at the specified assessment time points. Improvement relative to the subject's condition at the initiation of the antidepressant treatment period (Phase A) will be assessed during the antidepressant treatment period (Phase A), and the improvement relative to the subject's condition at Week 8 of the antidepressant treatment period (Phase A) will be assessed during the double-blind period (Phase B) and the antidepressant-responder treatment-continuation period (Phase A+). The date, time, and results of assessment will be recorded in the source documents and the CRF.

0. Not assessed 1. Very much improved 2. Much improved 3. Minimally improved

4. No change 5. Minimally worse 6. Much worse 7. Very much worse

3.7.2.3 Clinical Global Impression - Severity of Illness

(1) Time points

At screening, the initiation and Weeks 1, 2, 3, 4, 6, and 8 (or discontinuation) of the antidepressant treatment period (Phase A), Weeks 1, 2, 3, 4, 5, and 6 (or discontinuation) of the double-blind period (Phase B), and Week 6 (or discontinuation) of the antidepressant-responder treatment-continuation period (Phase A+)

(2) Methods

The investigator or subinvestigator will assess the severity of the subject's depressive symptoms on the following 8-point scale using CGI-S at the specified assessment time points, and record the date, time, and results of assessment in the source documents and the CRF.

0. Not assessed 1. Normal, not at all ill 2. Borderline mentally ill 3. Mildly ill

4. Moderately ill 5. Markedly ill 6. Severely ill

7. Among the most extremely ill patients

3.7.2.4 Hamilton Rating Scale for Depression

(1) Time points

At screening, the initiation and Week 8 (or discontinuation) of the antidepressant treatment period (Phase A), Week 6 (or discontinuation) of the double-blind period (Phase B), and Week 6 (or discontinuation) of the antidepressant-responder treatment-continuation period (Phase A+)

(2) Methods

A trained and qualified investigator or subinvestigator will assess the following 21 symptoms of depression in the subject on a 5-point scale (0 to 4) for Items No. 1, 2, 10 to 14, 16 to 17, and 19, on a 4-point scale (0 to 3) for Items No. 5 and 20, and on a 3-point scale (0 to 2) for Items No. 3, 4, 6 to 9, 15, 18, and 21 using the Structured Interview Guide for HAM-D (SIGH-D) at the specified assessment time points, and calculate the total score for Items No. 1 to 17, and record the date, time, and results of assessment in the source documents and the CRF.

Protocol 331-102-00058

| 1. Depressed mood | Work and activities | 3. Genital symptoms |
|-------------------|---------------------------------------|---------------------|
| 1. Debressed mood | 2. WOIR and activities | J. Ochitai symbioms |

4. Somatic symptoms gastrointestinal 5. Loss of weight 6. Early (initial) insomnia

7. Middle insomnia 8. Late (terminal) insomnia 9. Somatic symptoms general

10. Feelings of guilt 11. Suicide 12. Anxiety psychic 13. Anxiety somatic

14. Hypochondriasis 15. Insight 16. Retardation 17. Agitation

18. Diurnal variation 19. Depersonalization and derealization 20. Paranoid symptoms

21. Obsessional and compulsive symptoms

3.7.2.5 Sheehan Disability Scale

(1) Time Points

At the initiation and Week 8 (or discontinuation) of the antidepressant treatment period (Phase A), Weeks 3 and 6 (or discontinuation) of the double-blind period (Phase B), and Week 6 (or discontinuation) of the antidepressant-responder treatment-continuation period (Phase A+)

(2) Methods

The investigator or subinvestigator will use SDS at the specified assessment time points and ask subjects to self-rate the degree of impairment for each of 3 items ("work/school," "social life," and "family life/home responsibilities") on an 11-point scale ranging from 0 (not at all) to 10 (extremely) and the number of "days lost" and "days unproductive" caused by symptoms in the past week. The investigator or subinvestigator will record the date, time, and results of assessment in the source documents and the CRF.

3.7.2.6 Montgomery Asberg Depression Rating Scale Self-assessment

(1) Time points

At the initiation and Weeks 2, 4, 6, and 8 (or discontinuation) of the antidepressant treatment period (Phase A), Weeks 1, 2, 3, 4, 5, and 6 (or discontinuation) of the double-blind period (Phase B), and Week 6 (or discontinuation) of the antidepressant-responder treatment-continuation period (Phase A+)

(2) Methods

All subjects will self-assess each of the following 10 MADRS-S items, selecting the applicable level on a scale from 0 to 3 at the specified assessment time points. The investigator or subinvestigator will record the date, time, and results of assessment in the source documents and the CRF.

Protocol 331-102-00058

Staying power 1. Mood 2. Feelings of unease 3. Sleep 4. Appetite 5. Ability to concentrate 6. Initiative 7. Emotional involvement 8. Pessimism 9. Zest for life

3.7.3 Safety Assessments

3.7.3.1 Adverse Events

Refer to Section 5, Reporting of Adverse Events.

3.7.3.2 Clinical Laboratory Assessments

(1) Time Points

At screening (in the fasting state to the extent possible), Week 8 (in the fasting state) or at discontinuation (in the fasting state to the extent possible) of the antidepressant treatment period (Phase A), Week 3 (in the fasting state to the extent possible) and Week 6 (in the fasting state) or at discontinuation (preferably in the fasting state) of the double-blind period (Phase B), and Week 6 (in the fasting state) or at discontinuation (in the fasting state to the extent possible) of the antidepressant-responder treatment-continuation period (Phase A+)

(2) Methods

Subjects will be asked to visit the trial site in the fasting state (a fast for at least 8 hours [including drinks containing sugar, such as juice]) at Week 8 of the antidepressant treatment period (Phase A) and Week 6 of the double-blind period (Phase B) or the antidepressant-responder treatment-continuation period (Phase A+) and in the fasting state to the extent possible at other time points including examinations at discontinuation.

Blood and urine samples will be collected from each subject at the time of clinical laboratory tests as specified in the assessment schedules shown in Table 3.7-1 through Table 3.7-3, and the date and time of blood sampling and the date of urine sampling as well as the fasting or fed state during blood sampling will be recorded in the source documents and the CRF. In this trial, the central laboratory selected by the sponsor will be used. Clinical laboratory test values determined at the central laboratory will be used for eligibility assessment. For appropriate procedures for the collection, handling, and shipment of samples, separately documented procedures will be prepared and provided prior to the start of the trial. The central laboratory will report the results of tests to the investigator or subinvestigator. The investigator or subinvestigator will confirm the results of tests and date and sign the clinical laboratory test report to make it an official document. The results of laboratory tests, which will be reported directly from the central

laboratory to the sponsor as an electronic file, do not need to be recorded in the source documents or the CRF.

| Table 3.7.3.2-1 Clinical Laboratory Assessments | | | | |
|---|---|--|--|--|
| Hematology: | Serum chemistry: | | | |
| Red Blood Cell count | AST (Glutamic oxaloacetic transaminase [GOT]) | | | |
| White blood cell count | ALT (Glutamic pyruvic transaminase [GPT]) | | | |
| Differential count of white blood cells (neutrophils, | Alkaline Phosphatase (ALP) | | | |
| eosinophils, basophils, monocytes, and lymphocytes) | Lactic Dehydrogenase (LDH) | | | |
| Platelet count | Gamma-glutamyl transpeptidase (γ-GTP) | | | |
| Hemoglobin | Total protein | | | |
| Hematocrit | Albumin | | | |
| | Total bilirubin | | | |
| Urinalysis: | Cholesterol (total cholesterol, low-density | | | |
| pН | lipoprotein [LDL] cholesterol, and high-density | | | |
| Protein | lipoprotein [HDL] cholesterol) | | | |
| Glucose | Triglycerides | | | |
| Occult blood | Blood urea nitrogen (BUN) | | | |
| Urobilinogen | Creatinine | | | |
| Specific gravity | Uric acid | | | |
| Ketone body | Creatine kinase (CK) (CPK) | | | |
| | Serum electrolytes (Na, K, Cl, Ca, Mg, P, | | | |
| | bicarbonate) | | | |
| | Blood glucose | | | |
| | HbA1c (NGSP value) | | | |
| | Prothrombin time (PT) | | | |
| | Activated partial thromboplastin time (APTT) | | | |
| | PT (international normalized ratio [INR]) | | | |
| | Endocrinology: | | | |
| | Serum prolactin | | | |
| | Insulin | | | |
| | FT4 | | | |
| | TSH | | | |

To be performed in subjects in the fasting state (a fast for at least 8 hours [including drinks containing sugar, such as juice]) at Week 8 of the antidepressant treatment period (Phase A) and Week 6 of the double-blind period (Phase B) or the antidepressant-responder treatment-continuation period (Phase A+) and in the fasting state to the extent possible at other time points including examinations at discontinuation

3.7.3.3 Vital Signs and Physical Examination

(1) Vital signs

(a) Time points

At screening, the initiation and Weeks 1, 4, and 8 (or discontinuation) of the antidepressant treatment period (Phase A), Weeks 1, 2, 3, 4, 5, and 6 (or discontinuation) of the double-blind period (Phase B), and Weeks 1, 2, 3, 4, 5, and 6 (or discontinuation) of the antidepressant-responder treatment-continuation period (Phase A+)

(b) Methods

After keeping the subject in a relaxed state, body temperature will be measured and then blood pressure (systolic and diastolic) and pulse rate will be measured in the supine, sitting, and standing positions in accordance with the measurement methods specified by the trial site. For body temperature, the date and result of measurement will be recorded in the source documents and the CRF. Blood pressure and pulse rate will be measured in the supine, sitting, and standing positions, in this order, after maintaining each position for at least 3 minutes. The date, time, positions, and results of measurement will be recorded in the source documents and the CRF.

(2) Physical examination

(a) Time points

At screening, the initiation and Weeks 1, 2, 3, 4, 6, and 8 (or discontinuation) of the antidepressant treatment period (Phase A), Weeks 1, 2, 3, 4, 5, and 6 (or discontinuation) of the double-blind period (Phase B), post-treatment observation period, and Weeks 1, 2, 3, 4, 5, and 6 (or discontinuation) of the antidepressant-responder treatment-continuation period (Phase A+)

(b) Methods

The investigator or subinvestigator will perform a physical examination that includes the assessment items shown below through subject interview and other relevant methods and record the physical findings in the source documents. The date and results of examinations at screening and only the dates of examinations after the initiation of the antidepressant treatment period (Phase A) will be recorded in the source documents and the CRF. Any clinically significant physical findings compared with findings at screening are to be recorded as AEs.

Assessment items: HEENT (head, eyes, ears, nose, and throat), chest, abdomen, urogenital organs, limbs, nerves, and skin mucosa

(3) Waist circumference

(a) Time points

At the initiation and Week 8 (or discontinuation) of the antidepressant treatment period (Phase A), Week 6 (or discontinuation) of the double-blind period (Phase B), and Week 6 (or discontinuation) of the antidepressant-responder treatment-continuation period (Phase A+)

(b) Methods

Measurement will be performed while the subject is minimally clothed (lightly clothed, removing heavy outer garments). The top of the hip bone and the upper edge of the right iliac crest will be located, and then a measuring tape will be placed horizontally all the way around the abdomen at the height of the iliac crest. Prior to measurement, the person engaged in measurement should ensure that the measuring tape is snug without indenting the subject's skin and is parallel to the floor. At the end of a normal expiration, waist circumference will be measured in centimeters (rounded off to the nearest whole number) and the date and result of measurement will be recorded in the source documents and the CRF.

(4) Height and body weight

(a) Time points

At screening, Week 8 (or discontinuation) of the antidepressant treatment period (Phase A), Week 6 (or discontinuation) of the double-blind period (Phase B), and Week 6 (or discontinuation) of the antidepressant-responder treatment-continuation period (Phase A+)

However, height will be measured only at screening.

(b) Methods

Body weight and height will be measured at the specified time points, and the date and results of measurement will be recorded in the source documents and the CRF (body weight in increments of 0.1 kg, height in increments of 0.1 cm). Body weight will be measured by the standard measurement method (fully clothed but without shoes) using a reliable, calibrated scale (the same scale should always be used to measure a particular subject).

3.7.3.4 12-lead Electrocardiography

(1) Time points

At screening, Week 8 (or discontinuation) of the antidepressant treatment period (Phase A), Week 6 (or discontinuation) of the double-blind period (Phase B), and Week 6 (or discontinuation) of the antidepressant-responder treatment-continuation period (Phase A+)

(2) Methods

The investigator or subinvestigator will record the subject's ECG using a 12-lead electrocardiograph supplied by the central ECG laboratory, assess whether the ECG

result is normal or abnormal, and record the date and time of ECG, normal/abnormal judgement, and abnormal findings in the source documents and the CRF. The original of the 12-lead ECG chart will be kept in the medical record or the investigator's file. The central ECG laboratory will collect 12-lead ECG data and measure heart rate, PR interval, RR interval, QRS interval, QT interval, and QT corrected for heart rate (QTc) [QTcB = QT interval/(RR interval)^{1/2}, QTcF = QT interval/(RR interval)^{1/3}, QTcN = QT interval/(RR interval)^{0.37}], and the physician of the central ECG laboratory will assess the data. The central ECG laboratory will report the results of analysis to the investigator or subinvestigator. The investigator or subinvestigator will confirm the results of analysis and date and sign the analysis result report to make it an official document. The investigator or subinvestigator will reconfirm the normal/abnormal judgement with reference to the analysis result report sent from the central ECG laboratory. The results of analysis, which will be reported directly from the central ECG laboratory to the sponsor as an electronic file, do not need to be recorded in the source documents or the CRF.

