5.2 Eliciting and Reporting Adverse Events

The investigator or subinvestigator will periodically assess subjects for the occurrence of AEs. To avoid bias in eliciting AEs, subjects should be asked the nonleading question: "How have you felt since your last visit?" For all AEs (serious and nonserious) reported by the subject, the event name, start and stop dates, severity, seriousness, relationship to IMP, actions taken regarding IMP administration, and outcome thereof must be recorded in the source documents and CRFs provided by the sponsor. Adverse event and SAE collection is to begin after a subject has signed the ICF. In this trial, AEs occurring during the screening period and the antidepressant treatment period (Phase A) will be assessed in comparison to the subject's condition at screening, and AEs occurring during the double-blind period (Phase B) and the antidepressant-responder treatment-continuation period (Phase A+) will be assessed in comparison to the subject's condition at Week 8 of the antidepressant treatment period (Phase A).

Use medical terminology in AE reporting. Adverse events should be reported as a single unifying diagnosis whenever possible or, in the absence of a unifying diagnosis, as individual signs or symptoms. Exacerbation or disease progression should be reported as an AE only if there are unusual or severe clinical features that were not present, or experienced earlier, or not expected based on the course of the condition. If a reported AE has worsened in severity or seriousness, it should be reported as a new AE on the CRF.

In addition, the sponsor must be notified immediately by e-mail, in principle, of any IREs according to the procedure outlined below, in Section 5.3 Immediately Reportable Events. Special attention should be paid to recording hospitalization and concomitant medications.

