7.6 Safety Analysis

Safety analysis for the double-blind period (Phase B) will be performed using the safety analysis set. Baseline is defined as Week 8 of the antidepressant treatment period (Phase A).

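### Protocol 3.7.3.3 compares Phase B physical findings with screening when deciding what is an AE, while 5.2 compares Phase B and Phase A+ AEs with Week 8 of Phase A; the two rules need to be reconciled

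*Protocol*

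**What the plan says.** Protocol 3.7.3.3(2) schedules physical examinations from screening onwards, including "Weeks 1, 2, 3, 4, 5, and 6 (or discontinuation) of the double-blind period (Phase B), post-treatment observation period" and the weekly Phase A+ visits. For all of them it gives a single rule: "Any clinically significant physical findings compared with findings at screening are to be recorded as AEs". Investigators are to "record the physical findings in the source documents". The CRF takes the results of the screening examination, but "only the dates of examinations after the initiation of the antidepressant treatment period (Phase A) will be recorded" for the later ones.

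Protocol 5.2 sets the reference by period. AEs in the screening period and Phase A "will be assessed in comparison to the subject's condition at screening". AEs in Phase B and Phase A+ "will be assessed in comparison to the subject's condition at Week 8 of the antidepressant treatment period (Phase A"). It names no reference for the post-treatment observation period.

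Three other places bear on the point:
- Protocol 3.7.3.1, the adverse-event entry among the safety assessments, says only: "Refer to Section 5, Reporting of Adverse Events".
- Protocol 7.6, on the Phase B safety analysis, states: "Baseline is defined as Week 8 of the antidepressant treatment period (Phase A").
- Protocol 7.6.1 and SAP 9.2 define a TEAE by its occurrence after Phase B dosing has started.

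**The concern.** Both sections are instructions to the same investigator about the same Phase B examination, and they name different reference states. Neither says which prevails. The pointer in 3.7.3.1 sends AEs in general to Section 5, but 3.7.3.3 carries its own AE rule for physical findings. A site could follow either one in good faith, and the synopsis plans 170 sites.

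The two reference states can differ. Between screening and Week 8 the previous antidepressant is tapered (3.7.1.2) and a different one is given for eight weeks (3.7.1.4). Randomised treatment starts only after that. The protocol shifts the reference explicitly elsewhere: in 3.7.2.2, CGI-I is rated against the start of Phase A during Phase A and against Week 8 during Phase B. The physical-examination sentence has no such shift.

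What is at stake is whether physical findings enter the Phase B TEAE tables by the same rule at every site. After screening, the AE page is the only way such a finding reaches the CRF, so the sponsor could not see from the CRF which rule a site had used.

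**Working it through.** The plan gives no figure on this point, so there is none to reproduce. The check is to apply each rule, read alone, to a clinically significant sign seen at a Phase B examination, for every combination of presence at screening and at Week 8 of Phase A.

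| Pattern | At screening | At Week 8 | In Phase B | 3.7.3.3 (versus screening) | 5.2 (versus Week 8) |
|---|---|---|---|---|---|
| 1 | absent | absent | present | AE | AE |
| 2 | present | present, unchanged | present, unchanged | not an AE | not an AE |
| 3 | present | absent | present | not an AE | AE |
| 4 | absent | present | present, unchanged | AE | not a new AE |

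The rules disagree in 2 of the 4 patterns.

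**Pattern 3.** A site that uses 3.7.3.3 alone sees no change from screening and has no instruction to make an AE entry. A site that uses 5.2 enters an AE with a Phase B onset, which is a TEAE.

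**Pattern 4.** The sign was new in Phase A. Both sections use screening as the reference in Phase A, so it should already be an AE with a Phase A start date. Section 5.2 calls for a new entry when a reported AE worsens in severity or seriousness, and this one has not. It reaches the TEAE tables only if a site, again noting a difference from screening, enters it a second time with a Phase B onset.

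**Distance between the reference points.** Table 3.7.1.9-1 allows screening from Day -28 and the Week 8 visit up to Day 57 + 2 = Day 59. With no Day 0, the longest gap is 28 + 58 = 86 days. This shows only that the subject's condition has time to change. It does not say how often patterns 3 and 4 occur, and the documents give nothing from which to estimate that.

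**Post-treatment visit.** 3.7.3.3 schedules an examination here and applies the screening rule, while 5.2 gives no reference. The period matters for reporting because the SAP 9.2 table of TEAEs by date of first onset has a category for onset after trial treatment.

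**The case against.** The strongest reply is that 3.7.3.3 says which findings must be recorded and does not say that no others are AEs. Section 5.1 defines an AE broadly and Section 5 governs reporting, so a careful site would record pattern 3 anyway. This is a fair reading and it limits the consequence: the finding is missed only at a site that takes 3.7.3.3 as the whole rule. It does not remove the conflict, because nothing in the text rules that reading out.

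A reader might also infer several stronger things that the documents do not support.

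- *Signs that return on study drug go unrecorded.* They are written in the source documents, and they remain AEs at any site that applies 5.2. Extrapyramidal signs, vital signs, weight, waist circumference and ECG are also measured and analysed separately (Protocol 7.6.3 to 7.6.5).
- *Background antidepressant effects are added to every arm and dilute the treatment difference.* That requires sites to re-enter unchanged Phase A signs with a new onset date, which 5.2 does not ask for.
- *5.2 cannot be applied because Week 8 findings are not in the database.* The investigator applies 5.2 at the site, from the source documents.
- *The Week 8 safety baseline in 7.6 is breached.* Physical examination data are only listed (Protocol 7.6.3, SAP 9.5), with no change-from-baseline analysis. That baseline barely acts on them. The effect runs through AE recording.
- *The size is 720 x 6 = 4320 examinations.* That is the number of scheduled weekly Phase B examinations with no dropout. It is not a count of affected findings.

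**Conclusion.** The inconsistency is real and narrow. For Phase B and Phase A+ physical findings, 3.7.3.3(2) and 5.2 name different references, and they give different answers in two of four patterns. AE recording from physical examinations may therefore vary between sites. In pattern 3 an AE can be missed; in pattern 4 a TEAE can be added only through re-entry. The number of findings affected cannot be derived. The primary analysis, the power and the stated sample size are not affected.

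The conclusion assumes that some sites would read the physical-examination sentence as complete in itself. The protocol neither says so nor prevents it. It also treats a sign as simply present or absent; a sign that changes in severity raises the same question of which reference applies. This is a wording conflict that merits correction because the correction is nearly free, not because a bias in the safety results has been shown.

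**What to change.** Reword the sentence in Protocol 3.7.3.3(2) so that clinically significant findings in the screening period and Phase A are compared with screening, and those in Phase B and Phase A+ with Week 8 of Phase A. That brings it into line with 5.2 as it stands.

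State the same Week 8 reference for the post-treatment observation visit in both 3.7.3.3 and 5.2. This part extends 5.2, which is silent there, so it should be written as a deliberate addition.

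The cost is one reworded sentence, one short addition to each section, and a note to sites. No new assessment is needed, because the Week 8 examination is already scheduled. Entering its results in the CRF is optional: it would let the sponsor check the comparison centrally, but it is not needed to resolve the conflict.
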